Statistical analyses: **Primary outcome:** Due to COVID-19’s impact on this study’s initial primary outcome of the number of participants that were tested for HIV at the 6 month timepoint, the primary outcome has been modified. Behavioral outcomes are influenced by attitudes and intentions; therefore, we will explore attitudes and intentions in our study, with **attitudes about around HTC** as the new primary outcome. After a thorough review of existing literature, the team decided that the primary outcome would be changed to measuring participant’s attitudes around HTC at 6 months for the full cohort, with intentions and behaviors being assessed as secondary outcomes. **Secondary outcomes:** To address the secondary outcomes we will use repeated measures ANCOVAs (with Bonferroni corrections to account for multiple statistical tests). The models will include attitudes, perceived barriers, perceived norms, intentions, self-efficacy, and knowledge as dependent variables, with study condition as the independent variable, and sex, ethnicity, and history of testing as covariates. **Mediators and moderators:** Data will be collected on potential mediators and moderators and examined using conventional methods¹¹³. Baseline levels of these mediators and moderators will be used in the models to assess whether these variables affect the primary or secondary outcomes. In addition, because these variables might change over time during participation in the study, they will also be considered as time-varying covariates. **Mediators:** Based on our logic model¹² that will guide the development of the proposed intervention, we predict that 1) attitudes, 2) perceived barriers, 3) perceived norms, 4) intentions, 5) self-efficacy, and 6) knowledge will mediate the effects of the intervention on HTC at 6 months. The selection of mediators is based upon the logic model and given the proposed game will have many different components (as our current *PlayForward* game does), and given our experience of including all of these components into a game intervention, this selection of mediators was carefully guided by the process of constructing the logic model. We will use the criteria proposed by Baron and Kenny (1986)¹¹³ to test the relationships among the outcomes and presumed mediators. According to these criteria, four conditions should be met to establish mediation. We outline these conditions using our specific hypothesis that intentions mediate the relationship between the study condition (intervention or control) and HTC as an example. The first condition is that the study condition is directly related to HTC. Second, the intervention condition has a direct effect on the mediator (intentions). Third, intentions have a direct effect on HTC, when the study condition is controlled. Fourth, if intentions mediate the intervention condition-HTC relationship, the direct effect of the study condition on HTC is reduced or eliminated after controlling for intentions. To test the significance of mediation effect, which is called indirect effect, we will calculate Sobel's test¹¹⁴⁻¹¹⁶ for each proposed mediator. Sobel's test determines the significance of the mediation effect by testing the null hypothesis that the indirect effect coefficient is zero (i.e. whether the indirect effect of the independent variable on the dependent variables is significantly different from zero). **Moderators:** Variables that predict the outcome variable (first substance use) differently between treatments will be considered to be moderators using the model outlined by Kraemer et al¹¹⁷. In order to be considered a moderator, the variable must be present prior to randomization and must not be related to the independent variable (*PlayTest!* vs. control games). Pre-randomization variables that interact with the independent variable in predicting the outcome variable (HTC) will be considered moderators of treatment. Variables that predict the outcome variable but do not significantly interact with treatment condition will be classified as nonspecific pre-randomization predictors.

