
Collection and analysis of the in-game data: We will build on systems we have developed to analyze the data collected by the game software or the in-game data⁹⁸, which will serve as the foundation for analytics system built into the game. Briefly, using Player Game State Data (the traditional save/load data so a player can save their progress and pick up later where they left off) and Activity Logging Data (the relevant time-stamped player

actions during gameplay), we will examine the paths taken and decisions made by each player, documenting their exposure to content and the “learning curve” from the in-game data.

All data collected from the assessments will be entered directly into the secure web-based system, OnCore, Yale’s enterprise-wide clinical research management system. OnCore is a fully integrated system development by Forte, which includes three modules: 1) Clinical research management (CRM); 2) Bio-specimen management (BSM); and 3) Patient registry. This project will utilize the CRM module as the electronic data capture system for all case report form data and to support subject tracking. Data will be entered into the OnCore system either by research staff, or with the more sensitive assessments, by the participant themselves. This method limits data entry-associated errors. Before enrolling participants into the intervention, we will conduct a pilot test with two to three participants to assess acceptability and usability of the game, make changes as needed, and confirm data collection procedures.

New proposed plan for analysis approach due to COVID-19

1. Revise power calculations to ensure that a clinically meaningful effect size for the new primary outcome (attitudes around HTC at 6 months in the full cohort) can be detected.
2. Examine **attitudes** around HTC as primary outcome at 6 months in the full cohort.
3. Examine **intentions** to get tested at 6 months in full cohort.
4. Examine **HTC** at 6 months in smaller cohort of students that were able to reach the full 6 months of the study without being impacted by the pandemic (N=135). This study is not powered to detect a difference at this smaller sample size.

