5. Examine **HTC** at 3 months for a sub-cohort of students who were able to reach that time point without being affected by the pandemic (N=237; the study is powered for this outcome at n=236, but at 6 months). While we technically would be powered at this time-point, we would have cut our time to reach the outcome in half, posing a considerable limitation.
6. Examine attitudes and intentions at 3 months (N=237) (to be used in conjunction w #4 directly above).

New data analysis plan suggestion from study's Data Safety Monitoring Board member

- Use mixed models for the repeated measures analyses of the dimensional outcomes, as they use all available data on an individual and are generally robust to data missing at random. The repeated measures ANOVA approach that is mentioned in the document is meant for complete data and is not flexible in accounting for the correlations within individual.

SECTION II: RESEARCH INVOLVING DRUGS, BIOLOGICS, RADIOTRACERS, PLACEBOS AND DEVICES

If this section (or one of its parts, A or B) is not applicable, check off N/A and delete the rest of the section.

A. RADIOTRACERS

N/A

1. Name of the radiotracer: *Write here*
2. Is the radiotracer FDA approved? YES NO

If NO, an FDA issued IND is required for the investigational use unless RDRC assumes oversight.

3. Check one: IND# *Write here* or RDRC oversight (RDRC approval will be required prior to use)

B. DRUGS/BIOLOGICS

N/A

1. If an **exemption from IND filing requirements is** sought for a clinical investigation of a drug product that is lawfully marketed in the United States, review the following categories and complete the category that applies (*and delete the inapplicable categories*):

Exempt Category 1: The clinical investigation of a drug product that is lawfully marketed in the United States can be exempt from IND regulations if all of the following are yes:

1. The intention of the investigation is NOT to report to the FDA as a well-controlled study in support of a new indication for use or to be used to support any other significant change in the labeling for the drug.	
2. The drug that is undergoing investigation is lawfully marketed as a prescription drug product, and the intention of the investigation is NOT to support a significant change in the advertising for the product.	

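### The new primary outcome, attitudes at 6 months, has no assigned model or month-6 contrast; the only committed model is the secondary ANCOVA, and the mixed model is only suggested

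*Combined protocol and SAP*

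**What the plan says.** Because of COVID-19, item 13 (Statistical Considerations, Phase II) replaces HIV testing and counseling (HTC) as primary outcome with "attitudes around HTC at 6 months for the full cohort, with intentions and behaviors being assessed as secondary outcomes". The text then passes directly to the secondary outcomes. These are to be analysed by repeated measures ANCOVAs with Bonferroni correction, and attitudes is still among the outcomes listed: "The models will include attitudes, perceived barriers, perceived norms, intentions, self-efficacy, and knowledge as dependent variables". The explanatory terms of these ANCOVAs are then given, and no baseline score is among them: "with study condition as the independent variable, and sex, ethnicity, and history of testing as covariates".

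Under mediators and moderators, the same item adds: "Baseline levels of these mediators and moderators will be used in the models".

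The COVID-19 analysis plan that follows has two relevant items:
- Item 1 is still to be done: "Revise power calculations to ensure that a clinically meaningful effect size for the new primary outcome".
- Item 2 says only to examine attitudes "around HTC as primary outcome at 6 months in the full cohort". Attitudes at 3 months is a separate entry, item 6.

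Next comes a paragraph headed as a suggestion from a Data Safety Monitoring Board member: "Use mixed models for the repeated measures analyses of the dimensional outcomes". Its reason is that the repeated measures approach in the document is meant for complete data.

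Item 4 (Research Plan) assumes 80% retention at 6 months. Table 1 schedules two attitude measures at baseline, week 4, month 3 and month 6: *Attitudes About HIV* and *Attitudes about STI and HIV Testing*.

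**The concern.** The former primary outcome had a named test, sidedness and level: Fisher's exact test, two-sided, 0.05 (item 4, Statistical analyses). When the outcome was changed, that analysis fell away and nothing was written in its place.

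The one model the plan commits to for attitudes belongs to the secondary outcomes, so the primary variable also sits in the Bonferroni-corrected family. The better-suited model is described but not adopted.

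Several choices therefore remain open on a primary outcome that was changed during the trial: which model is primary, which arm contrast is tested, whether the baseline score is adjusted for, and how missing month-6 scores are handled. If they are settled after arm-level results are seen, the primary result loses its pre-specified standing. Precision from a baseline score that is already collected may also be given up, and a complete-data analysis can be biased if loss depends on earlier scores.

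**Working it through.** **What each candidate text supplies for attitudes at month 6**

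| Text | Applies to | Month-6 contrast | Baseline attitude score | Missing scores |
|---|---|---|---|---|
| Item 13, primary outcome | attitudes, 6 months | none | not mentioned | not mentioned |
| Item 13, ANCOVA | secondary outcomes, attitudes included | none | not in covariate list | complete data, according to the board member |
| Item 13, mediators and moderators | mediator and moderator models | none | used there | not mentioned |
| Board member's suggestion | dimensional outcomes | none | not mentioned | uses all available data |

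As usually fitted, the arm term of a repeated measures model averages over the visits included, and the arm-by-visit term asks whether the difference changes. Neither is the month-6 difference, so the contrast has to be written down.

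**The plan's own figures.** None is given for attitudes. For HTC, item 4 states 118 per group, from an effect size of 0.27, 85% power and alpha 0.05. The dropout step reproduces: 118/0.8 = 147.5, so 148 per arm and 296 in all. The 118 does not follow if 0.27 is a standardised mean difference: 2 × (1.960 + 1.036)²/0.27² = 246.3, so 247 per arm. The metric is not named, so 118 cannot be verified rather than being shown wrong. It serves below only as an assumed number of evaluable participants.

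**Baseline adjustment.** Assumptions: SD 1, two-sided 0.05, normal approximation, baseline-to-month-6 correlation ρ. The documents give no SD or correlation for attitudes.
- Standard error without baseline: √(2/n) = √(2/118) = 0.130.
- Standard error with baseline: √((2/n)(1 − ρ²)).
- Difference detectable with 85% power: (1.960 + 1.036) × standard error.

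| | No baseline | ρ = 0.3 | ρ = 0.5 | ρ = 0.7 |
|---|---|---|---|---|
| Detectable difference (SD) | 0.390 | 0.372 | 0.338 | 0.279 |

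**Missing month-6 scores.** At the assumed retention, 296 × 0.8 = 236.8, so about 237 have month 6 and 59 do not. The mixed model keeps those with at least one follow-up score and does not recover the rest. If losses reach 7%, 13% and 20% by week 4, month 3 and month 6 (an assumed split), 296 × 0.93 gives about 275 contributing, and 21 are not recovered.

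A simulation used 148 per arm, compound symmetry, a true effect of 0.39 SD at every visit and 4,000 runs per ρ. The mixed-model estimate was obtained by sequential regression, which is the maximum likelihood solution under monotone loss.

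| | ρ = 0.3 | ρ = 0.5 | ρ = 0.7 |
|---|---|---|---|
| Random loss: power, baseline-adjusted completers | 87.4% | 93.1% | 98.3% |
| Random loss: power, mixed model | 87.7% | 93.2% | 98.6% |
| Score-dependent loss in one arm: estimate, unadjusted completers | 0.455 | 0.491 | 0.533 |
| Same: estimate, baseline-adjusted completers | 0.420 | 0.423 | 0.421 |
| Same: estimate, mixed model | 0.389 | 0.387 | 0.392 |

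In the score-dependent rows, loss was weighted by exp(−last score).

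**The case against.** The strongest reply is that the intent can be seen. Time point and cohort are fixed, all analyses follow intent-to-treat, and the mixed-model paragraph is the last analysis text in item 13, is worded as an instruction and covers the dimensional outcomes. On this view only a wording repair is missing. Much of that stands, and it is why this is not a more serious defect. It does not remove the conflict: the paragraph is headed a suggestion, the ANCOVA text remains, and neither names the month-6 contrast.

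Some stronger readings are tempting but not supported:
- **That the primary test has no level, or only a Bonferroni share.** Two-sided 0.05 is the natural carry-over from the Phase II text in item 4. The plan states neither a family size nor a correction applied to the primary test.
- **That the scale is wholly open.** Of the two attitude rows in Table 1, only *Attitudes about STI and HIV Testing* names testing. It also covers STI testing, so confirmation is sensible, but it is the evident choice.
- **That the baseline score is certainly unused.** A repeated measures model may carry baseline as a time level. The text simply does not say so.
- **That the tabulated gain is a loss under this plan.** The comparator, a month-6 comparison without baseline, is not something the plan proposes.

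The score-dependent loss pattern was also constructed, and is of the kind a mixed model handles by design. It shows the direction of the risk, not its likely size here.

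**Conclusion.** The concern holds as a point that should be fixed. The declared primary outcome has no adopted model and no stated month-6 contrast, and attitudes appears in both the primary and the secondary set. The document also carries a criticism of its only committed model for this variable without resolving it.

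The conclusion rests on the text. The figures only indicate size, and they depend on an assumed correlation, on a sample size set for HTC, and on 80% retention. With those assumptions, baseline adjustment lowers the detectable difference by between 0.02 SD (ρ = 0.3) and 0.11 SD (ρ = 0.7). The mixed model's further gain in power under random loss is at most 0.3 points in the simulation. Its main value is protection when loss depends on earlier scores.

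A reader might infer that the primary test cannot be run at all. That goes too far: time point, cohort, arms and level are settled, and the scale and model family can reasonably be inferred.

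**What to change.** Before arm-level results are seen:
1. Adopt the mixed model as the primary analysis and say so. Use all week 4, month 3 and month 6 attitude scores, with arm, visit, arm-by-visit, baseline attitude score, sex, ethnicity and testing history.
2. Name the primary test: the arm contrast at month 6, two-sided 0.05.
3. Confirm *Attitudes about STI and HIV Testing* as the primary scale, and use the same scale as the baseline covariate.
4. Remove attitudes from the secondary Bonferroni list, and replace the ANCOVA text in items 4 and 13.
5. Correct the places that still name HTC as primary: item 4 (data collection and management, and Statistical analyses) and Section IV, question 2.

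The cost is SAP wording, modest code and one confirmation by the study team. No new data are needed, because Table 1 already schedules the scores.

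There is one statistical price. If the effect is constant over follow-up, the month-6 contrast has less power than a follow-up average. At ρ = 0.5, 118 per arm and 0.39 SD, the baseline-adjusted average has variance (2/118) × ((1 + 2 × 0.5)/3 − 0.5²) = 0.00706 and power 99.6%, against 93.3% for the baseline-adjusted month-6 contrast. That is the price of testing the endpoint the plan declares.

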Adequacy of sample size: A sample size calculation was done using the G*Power software. An effect size of 0.27, was estimated (conservatively) based on previous research¹⁰³. With equal numbers of subjects in each group, and alpha = 0.05, to provide 85% power to detect a difference in HTC rates at six months controlling for history of testing, sex, and ethnicity, a sample of 118 per group (total N = 236) is required. Based on adherence rates from our test of the original ***PlayForward*** game we assume 80% retention at 6 months. To account for the 20% dropout we will seek to enroll 296 participants.

Randomization: We will use a stratified randomization procedure¹⁰⁴ to assign participants to one of the study arms. Gender, race/ethnicity, and age will be included in the randomization algorithm because these variables have been found to be important predictors of HTC in adolescents¹⁰³. The stratification would be as follows two gender groups (girl vs. boy), two ethnic groups (Hispanic vs. non-Hispanic), three groups for race (White, African-American, Other) and two groups for age – (14, 15, 16 vs. 17 and 18). A block size of 6 will be used for the stratification process.

Treatment conditions: The research staff will orient the participants to the use of either ***PlayTest!*** or the control videogames. Players in both groups will play through an online tutorial demonstrating the mechanics of the game. Each player will use a dedicated device to access their game on the web and a set of headphones that they will use during each gameplay session. The research staff will oversee all gameplay to ensure that participants are playing and to field any questions. The control videogames (**see below**) will be engaging and fun but will be devoid of relevant content.

Assessments: We will assess participant characteristics (demographic), outcomes, and process measures (Table 1). For outcomes, we will collect data on actual HTC and assess a variety of mediators and moderators among teens (e.g., attitudes, intentions, knowledge). To measure actual testing in our participants, we will work with health care professionals at school clinics located on the premises of our partner sites to determine if students who participated in our study subsequently got tested. This data will be collected based on the protocol of the specific clinic, and the participants’ personal health information will be de-identified (including results) before being

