- ⊕ At the end of each month, the facilitator will check the *Student Identification Form* to identify any students that have utilized the school based health center during that month.
 - If a student has used the health center, then the facilitator will record pertinent information on the *Health Center Participation Form* that is on the password protected excel document for the monthly time period in review.
- ⊕ At the end of each month, the facilitator will meet with a member of the play2PREVENT team for approximately 10-15 minutes. During this brief meeting the SBHC facilitator and the play2PREVENT team member will print the *Health Center Participation Form* for the time period at hand and both parties will sign-off on its completeness. The printed sheet will then be placed in the secured lockbox with the USB drive.
- ⊕ Use the 3000z billing code for participants that come in for a STI/HIV test to protect privacy during insurance billing.

Data analysis

Phase 2: Data analyses general considerations: All statistical analyses will be conducted based on the “intent-to-treat” principle, through the use of either SPSS or SAS statistical packages.

Statistical analyses: **Primary outcome:** The primary outcome will be the proportion of participants who engage in HTC within the six-month study period. Rates of HTC among intervention and control participants at six months will be compared using Fisher’s exact test and a 2-sided test at the 0.05 level. **Secondary outcomes:** To address the secondary outcomes we will use repeated measures ANCOVAs (with Bonferroni corrections to account for multiple statistical tests). The models will include attitudes, perceived barriers, perceived norms, intentions, self-efficacy, and knowledge as dependent variables, with study condition as the independent variable, and sex, ethnicity, and history of testing as covariates. **Mediators and moderators:** Data will be collected on potential mediators and moderators and examined using conventional methods¹¹³. Baseline levels of these mediators and moderators will be used in the models to assess whether these variables affect the primary or secondary outcomes. In addition, because these variables might change over time during participation in the study, they will also be considered as time-varying covariates. **Mediators:** Based on our logic model¹¹² that will guide the development of the proposed intervention, we predict that 1) attitudes, 2) perceived barriers, 3)

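### Secondary outcomes are corrected by single-step Bonferroni; the Holm step-down gives the same family-wise error guarantee and never rejects less, so some power is given up for nothing the plan asks for

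*Combined protocol and SAP*

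**What the plan says.** Section 13 (Statistical Considerations), under the Phase II data analysis strategy, says of the secondary outcomes: "we will use repeated measures ANCOVAs (with Bonferroni corrections to account for multiple statistical tests". Section 4 (Research Plan), under Data analysis, has the same sentence. In both places the next sentence gives the outcomes: "The models will include attitudes, perceived barriers, perceived norms, intentions, self-efficacy, and knowledge as dependent variables".

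Section 13 also carries the COVID-19 revision, under which "the primary outcome would be changed to measuring participant’s attitudes around HTC at 6 months for the full cohort". The revision then places two other outcomes below that one, "with intentions and behaviors being assessed as secondary outcomes". Attitudes is therefore both the primary outcome and one of the six listed dependent variables. Behaviors is secondary but is not among the six. Section 4 still describes HTC as primary.

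The plan does not give the number of tests in the family or an adjusted significance level. It does not say whether the correction runs across outcomes, time points or both. The mixed-model suggestion at the end of Section 13 leaves multiplicity untouched. No step-down method appears, simultaneous confidence intervals are not promised, and no reason is given for choosing Bonferroni.

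**The concern.** Bonferroni holds every one of m tests to 0.05/m, however many of the others have already been rejected. Holm starts at the same threshold for the smallest p-value and relaxes it after each rejection. It makes the same guarantee and needs no assumption about correlation. Unless simultaneous intervals are wanted, nothing is gained by stopping at the single-step version.

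What is at stake is that a real effect on a secondary outcome, such as intentions, is reported as not significant when an equally rigorous procedure would have declared it. The plan's logic model predicts that all six listed constructs carry the intervention's effect on HTC. It thus expects several effects at once, which is the setting where a step-down gains most.

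**Working it through.** **The plan's own figure.** No power or adjusted level is stated for the secondary outcomes, so there is no figure on this point to reproduce. The nearest is the sample size for the former primary outcome in Section 4, Adequacy of sample size: "An effect size of 0.27, was estimated (conservatively) based on previous research", "alpha = 0.05, to provide 85% power to detect a difference in HTC rates at six months", giving 118 per group. Read as a standardized mean difference with a two-sided test, 0.27 needs 2 × [(1.960 + 1.036)/0.27]² = 246.3, or 247 per group, and 118 per group would have Φ(0.27 × √59 − 1.960) = Φ(0.114) = 54.5% power. So 118 is not reproduced on that reading, and the plan does not state the metric. The dropout step agrees: 118/0.8 = 147.5, so 148 per arm and 296 in all. The present point does not depend on how 118 was derived.

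**Inputs.**
- From the plan: 118 evaluable per arm, equal allocation, level 0.05. The two-sided test is stated for the former primary outcome ("a 2-sided test at the 0.05 level") and assumed here for the secondary outcomes.
- Assumed: family size m = 6 (the list as written), 5 (attitudes removed) or 2 (intentions and behaviors only); correlation 0.5 between test statistics; equal true effects of d SD.
- Values of d: 0.27 borrows the plan's number, whose metric is unknown. 0.39 is what 118 per arm detects with 85% power: (1.960 + 1.036) × √(2/118) = 0.390.

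**Thresholds for m = 6.** Bonferroni: 0.05/6 = 0.00833 for all six tests. Holm, on ordered p-values: 0.00833, 0.0100, 0.0125, 0.0167, 0.025, 0.05, stopping at the first failure. Every Holm threshold is at least 0.00833, so anything Bonferroni rejects Holm also rejects.

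**Bonferroni power in closed form.** Per outcome, power ≈ Φ(d√(118/2) − z), with z the upper 0.025/m normal point.
- m = 6, z = 2.638: Φ(2.074 − 2.638) = 28.6% at 0.27 SD; Φ(2.996 − 2.638) = 64.0% at 0.39 SD.
- m = 2, z = 2.241: 43.3% and 77.5%.

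**Simulation** (correlated normal test statistics, at least 100,000 draws per scenario). Average power per true effect, Bonferroni → Holm:

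| m | Real effects | 0.27 SD | 0.39 SD |
|---|---|---|---|
| 6 | 6 | 29% → 35% | 64% → 74% |
| 6 | 3 | 29% → 30% | 64% → 67% |
| 6 | 1 | 29% → 29% | 64% → 64% |
| 5 | 5 | 31% → 37% | 66% → 76% |
| 2 | 2 | 43% → 48% | 77% → 82% |
| 2 | 1 | gain about 0.1 point | gain about 0.2 point |

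- *Correlation.* With six of six real at 0.39 SD, the gain is about 11 points at correlation 0.3 and about 10 at 0.7.
- *At least one rejection.* With six of six real the chance is the same under both methods: 65.1% at 0.27 SD and 93.4% at 0.39 SD.
- *Error.* With all six null, family-wise error is identical (about 4.2%). With three of six real at 0.39 SD, family-wise error on the null outcomes is about 2.3% under Bonferroni and 3.5% under Holm.
- *Dominance.* In no draw did Bonferroni reject a hypothesis that Holm did not.

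**The case against.** The strongest reply is that nothing here is wrong. Bonferroni is pre-specified, simple and conservative, the outcomes are secondary, and the primary analysis is unaffected. That stands, and it limits the point to an efficiency improvement.

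Four stronger readings are tempting, and the documents do not support them.
- *That the trial loses about ten points of power.* That needs all six effects real, equal and near 0.39 SD. The plan states no effect size or correlation for these outcomes, and with half the effects real the gain is 2 to 3 points. The simulation also uses one test per outcome and leaves out the repeated measures and covariates, so its power levels are illustrative.
- *That each test will be run at 0.0083.* The plan never sets m. The revised text could mean two secondary outcomes, and a correction attached to repeated measures ANCOVAs could be meant for comparisons between time points.
- *That Bonferroni buys no extra protection at all.* The guarantee is the same, but realised error on null outcomes is somewhat lower with Bonferroni when other effects are real. Both stay below 5%.
- *That all the listed outcomes gained weight when HTC ceased to be primary.* The revision names only intentions and behaviors as secondary; it does not raise barriers, norms, self-efficacy or knowledge.

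Bonferroni also has simple matching simultaneous intervals, whereas an unadjusted 95% interval can exclude zero beside a Holm-adjusted p-value above 0.05. That is a real but small cost, since the plan promises no simultaneous intervals.

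**Conclusion.** The point holds as an efficiency improvement. That Holm matches Bonferroni's guarantee and never rejects less is a mathematical fact that needs none of the assumptions above. Only the size of the gain rests on them (118 per arm, equal effects, correlation 0.5): from almost nothing with one real effect, through 2 to 3 points with three of six and about 5 points with two of two, to 6 points (0.27 SD) or 10 points (0.39 SD) with six of six. Holm helps with the second and later rejections; it does not make the first any easier when all effects are real.

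Neither method can be run as the text stands, because the family is undefined. The change of method and the definition of the family belong in one edit.

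**What to change.** In Section 13, Phase II secondary outcomes, replace the Bonferroni phrase by: *with the Holm step-down procedure at a family-wise two-sided 0.05*. Say that it applies to the treatment comparison at 6 months across a named list of secondary outcomes. Leave attitudes out of that list, since it is now primary, and state whether behaviors (HTC) is in it. Align the parallel sentence in Section 4, which still has HTC as primary, so that both sections describe the same family. Report Holm-adjusted p-values, with 95% confidence intervals labelled as unadjusted.

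The cost is one phrase in two places and a sentence naming the family, settled before outcomes are compared by arm. No data, visits or participants are added. Holm needs only ordered p-values, so it works with ANCOVA or mixed models, in SAS or by hand from SPSS output. The one drawback is that matching simultaneous intervals are less direct than with Bonferroni.
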